9.7.2.5.2 Secondary Endpoints and Evaluations

The secondary endpoints include the following:

- Description of the pattern of use of cabozantinib in real-life clinical settings:
 - starting dose and schedule
 - duration of cabozantinib treatment
 - treatment line
 - dose reductions and reasons
 - treatment interruption and reasons
 - treatment discontinuation and reasons
 - changes in the dose and schedule and reasons
 - concomitant radiotherapies
 - planned systemic therapy following cabozantinib discontinuation
 - median time to first dose modification due to AEs based on the investigator's decision (reduction, temporary interruption or discontinuation) together and for each component separately
 - mean and median daily dose of cabozantinib received, and dose intensity (average daily dose compared to starting dose)
 - mean and median numbers of any dose modification (reduction, temporary interruption, increase or discontinuation)
 - median time to any first dose modification (reduction, temporary interruption, increase or discontinuation) together and for each component separately
 - median time to end of treatment;
- Effectiveness assessment:
 - overall best response per investigator assessment
 - clinical and radiographic (assessed by the investigator based on RECIST 1.1 [10]) median PFS time defined as the time between the start date of cabozantinib and the date of progression or death
 - OS rate at the end of the study;
- Description of health care resource utilisation associated with the management of treatment-related AEs (as assessed by the investigator as certain, probable, possible or unlikely) during the treatment period:
 - number and duration of hospitalisations
 - number of surgical procedures
 - number of emergency room visits and intensive care unit stays
 - number of physician visits
 - number of homecare visits by nurse
 - concomitant medication (initiation or change to manage AEs)

PAGE 35 OF 58

• number of unplanned laboratory tests.

The secondary endpoints will be provided in listing format using the FAS and summarised descriptively using the FAS or the Safety populations, as appropriate, by line of treatment and in total.

In addition, the Kaplan-Meier method will be used to obtain the estimates of median PFS time, OS rate, median time to end of treatment, median time to first dose modification due to AEs based on the investigator's decision (temporary interruption, reduction or discontinuation) together and for each component separately and median time to any first dose modification (temporary interruption, reduction, increase or discontinuation) together and for each component separately and their associated 2-sided 95% CIs.

Concomitant medication will be coded using the World Health Organization Drug Dictionary (WHODRUG) and will be summarised with the number and percentage of subjects receiving concomitant medication by drug class and preferred drug name.

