- (7) Consents to participate in this noninterventional study.

There are no exclusion criteria for this study.

A total of 680 subjects are planned to be included: 340 subjects receiving second line therapy and 340 subjects receiving third and later line therapy.

The study population will consist of subjects diagnosed with advanced RCC, having received at least one prior VEGF-targeted therapy, who are starting cabozantinib tablets at the discretion of the treating physician and who consent to participate in the study. In order to avoid bias, participating physicians will be asked to include all successive eligible subjects except those who refuse the collection of and/or access to their data until 340 subjects have been included in each subgroup (second and third and later line therapy).

PAGE 13 OF 58

Cabozantinib is to be administered as directed by the investigator according to the study site's clinical practice and the Cabometyx™ Summary of Product Characteristics (SmPC).

In the METEOR study, the median duration of exposure in subjects receiving cabozantinib was 8.3 months (Inter-Quartile Range 4.2 to14.6). Subjects will be followed up to 30 days after discontinuation of cabozantinib with a maximum follow-up per subject of 12 months from treatment initiation, even if the subject continues to receive cabozantinib.

The end of the study will be the date of the last study visit for the last subject in the study.

The study will be conducted in countries where cabozantinib is marketed at the time of the study. It is anticipated that there will be approximately 100 study centres in 10 to 15 European countries.

Visits will take place according to the study site's clinical practice. During each data reporting period, the investigator will report data for the study endpoint assessments (see Table 1).

Variables

Only available evaluations as decided by the investigator based on local clinical practice will be collected in the study. See Table 1 for the schedule of assessments to be reported.

The data that will be collected are summarised below.

Demographic and baseline characteristics:

- Baseline demography: year of birth, gender;
- Use of tobacco, occupational status, sick leave status;

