9.2 Setting

The study will include subjects diagnosed with advanced RCC, having received at least one prior VEGF-targeted therapy, who are starting treatment with cabozantinib tablets at the discretion of the treating physician in the clinical setting (not as part of an interventional clinical study).

A total of 680 subjects are to be included in the study in countries where cabozantinib is marketed at the time of the study. It is planned to include equal numbers of subjects receiving second line therapy and third and later line therapy.

The study will follow the real-life management of patients in clinical practice. Visits will take place according to the study site's clinical practice. Cabozantinib is to be administered as directed by the investigator according to the study site's usual clinical practice and the Cabometyx™ Summary of Product Characteristics (SmPC). Only available evaluations as decided by the investigator based on local clinical practice will be collected. The investigator will report data for study endpoint assessments during the study data reporting periods (see Table 1 for a summary of the schedule of assessments to be reported).

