9.2.3 Study Population

The study population will consist of subjects diagnosed with advanced RCC, having received at least one prior VEGF-targeted therapy, who are starting cabozantinib tablets at the discretion of the treating physician and who consent to participate in the study.

In order to avoid bias related to physician-led subject selection, participating physicians will be asked to include all successive eligible subjects except those who refuse the collection of and/or access to their data until 340 subjects have been included in each subgroup (second and third and later line therapy).

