9.5 Study Size

The sample size is based on the primary endpoint which is the proportion of subjects with dose modifications due to AEs based on the investigator's decision (temporary interruption, dose reduction or discontinuation) assessed for each line of treatment (second line therapy or third and later line therapy). In the open-label METEOR Study, any dose reduction due to an AE occurred in 59.8% of subjects and the study drug was interrupted in 70% of subjects. Overall, at least one dose modification (i.e. reduction or interruption) was reported for 76% of subjects treated with cabozantinib. The rate of treatment discontinuation due to an AE was 9.7% for subjects treated with cabozantinib.

Assuming a dose modification proportion of 75%, a sample size of 289 subjects is required to estimate a 2-sided 95% level of confidence of the dose modification proportion with a precision of $\pm 5\%$. To have a precision of at least 5% in second line therapy and third and later line therapy, a minimum of 289 subjects must be included in each line of treatment (second line and third and later line).

Assuming that up to 15% subjects will start the treatment with cabozantinib using scheduled regimens different from the recommended regimen at initiation (60 mg/day) [8, 9], the total included population will represent 680 subjects.

The recruitment of subjects in the concerned subgroup will be closed as soon as the 340 subjects are reached.

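### The 340-per-line quotas set the second versus third-and-later split, so that part of the treatment-line endpoint does not describe practice in the full sample

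*Protocol*

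**What the plan says.** Section 9.7.2.5.2 (and the abstract, section 4) gives as a secondary endpoint the "Description of the pattern of use of cabozantinib in real-life clinical settings". One of its items is "treatment line". Secondary endpoints are summarised on the FAS or Safety population, by line and pooled.

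Section 9.2 states: "It is planned to include equal numbers of subjects receiving second line therapy and third and later line therapy". The abstract gives the numbers as "340 subjects receiving second line therapy and 340 subjects receiving third and later line therapy". Section 9.5 adds the closing rule: "The recruitment of subjects in the concerned subgroup will be closed as soon as the 340 subjects are reached". Section 9.2.3 asks physicians to include all successive eligible subjects, but only until each line has its 340.

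Section 9.9 (Limitations) repeats this quota-bounded consecutive inclusion as a protection against physician-led selection. It does not mention that the quota also fixes the mix of lines.

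**The concern.** A quantity set by the recruitment rule cannot also be an observation about practice. Once one line has closed, every further inclusion comes from the other line, and the sample is pulled towards 50:50 until both quotas are full. The second versus third-and-later share in the full FAS or Safety population then reflects the design.

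Section 7.2 motivates the study by saying that the real-world utilisation pattern is unknown. A half-and-half split tabulated under a real-life heading could be read as an answer to that question. The same fixed weights enter every pooled summary of an endpoint that differs between lines.

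**Working it through.** **The plan's own figures.** Inputs from section 9.5: "Assuming a dose modification proportion of 75%, a sample size of 289 subjects is required to estimate a 2-sided 95% level of confidence" with a precision of 5 points, and "Assuming that up to 15% subjects will start the treatment with cabozantinib using scheduled regimens different from the recommended regimen at initiation".

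- n = 1.96² × 0.75 × 0.25 / 0.05² = 288.1, rounded up to 289 per line.
- 289 / (1 − 0.15) = 340 per line; 2 × 340 = 680.

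All three figures reproduce. The quotas follow from the per-line precision target of the primary endpoint, and there is no sample-size error.

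**What the quotas do to the split.** With both filled, the second-line share is 340/680 = 50.0%. A nominal Clopper-Pearson 95% interval would be 46.2% to 53.8%, but it would say nothing about practice, because numerator and denominator are both fixed. The protocol does not specify an interval for this item.

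**Size of the discrepancy.** The protocol does not give the true second-line share s, so a range is assumed. Eligible starters needed to fill both quotas = 340 / min(s, 1 − s).

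| Assumed s | Reported | Reported minus true | Eligible starters needed | Arriving after their line closed |
|---|---|---|---|---|
| 30% | 50% | +20 points | 1134 | 454 |
| 40% | 50% | +10 | 850 | 170 |
| 50% | 50% | 0 | 680 | 0 |
| 60% | 50% | −10 | 850 | 170 |
| 70% | 50% | −20 | 1134 | 454 |

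**Pooled summaries.** Assume, for illustration, a proportion of 70% in second line and 80% in third and later line. The pooled figure by design is 0.5 × 70% + 0.5 × 80% = 75%. Weighted by the true mix it would run from 77% (s = 30%) to 73% (s = 70%).

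**What the data up to first closure can give.** Until the first line closes, inclusion is consecutive and open to both lines. The expected number included at that date is N = 340 / max(s, 1 − s), and the half-width for the share is 1.96 × √(s(1 − s)/N).

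| Assumed s | N at first closure | Half-width | Slower line, N − 340 |
|---|---|---|---|
| 55% | 618 | 3.9 points | 278 |
| 60% | 567 | 4.0 | 227 |
| 70% | 486 | 4.1 | 146 |
| 75% | 453 | 4.0 | 113 |

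The table is symmetric: a second-line share of 45% gives the same N as 55%, and so on. The half-widths ignore clustering by site.

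**The primary proportion in that window.** The slower line would have 278, 227, 146 or 113 subjects. After the 15% loss about 236, 193, 124 or 96 remain. At a proportion of 75% the half-widths are 1.96 × √(0.1875/n) = 5.5, 6.1, 7.6 and 8.7 points, against the planned 5.

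**The case against.** The strongest reply is that the line split is already the column heading of the tables. What the item can add is the actual line number (third, fourth and so on), which no quota fixes and which sections 9.3.1 and 9.3.2 collect. This stands. A reader might infer that treatment line cannot be estimated at all; the documents do not support that, because only the two-category split is fixed.

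It can also be said that the 340:340 target is stated openly several times and that table layout belongs to the statistical analysis plan. The first part is true. But the protocol itself sets both the endpoint and the quota, and nothing in it warns that the two conflict for this split.

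A reader might also infer that the by-line results are distorted by calendar time, since the last recruits all come from one line. The documents give little support for this. Both lines open together, so the faster line's recruitment period lies inside the slower line's. The analyses are descriptive without formal testing (section 9.7.2.1), and nothing in the protocol points to a time trend.

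Finally, inclusions before the first closure are not a sample of all practice. Sites are proposed by the sponsor's local medical teams (section 9.2.5), and patients who refuse data collection are left out (section 9.2.3). That stands too, and limits how the share may be labelled.

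**Conclusion.** The concern holds for the second versus third-and-later split and for pooled summaries read as real-life figures. If both quotas fill, the full-sample split is about 50:50 by design and does not estimate practice. Small departures through untreated subjects or missing safety follow-up, or larger ones if a quota is not filled, do not restore that meaning once one line has closed.

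For assumed second-line shares of 30% to 70%, the reported 50% is off by 0 to 20 points in either direction. A reader might infer that second-line use is understated. The protocol does not support a direction: a true share of 50% gives no error, and a majority of later-line starters reverses the sign.

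The primary endpoint per line, its precision and the sample size are untouched, and the quotas themselves are justified. This is a matter of interpretability in one secondary item, with a nearly free remedy.

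**What to change.** In section 9.7.2.5.2:

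1. Describe the second versus third-and-later share only from subjects included up to the date the first line quota closes. Label it as the mix among consenting consecutive starters at participating sites.
2. State that the full-sample split, and the 1:1 weighting of the pooled summaries, are set by design. Repeat this in section 9.9.
3. Report the distribution of line number within third and later line from the full sample.

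Recruitment, sample size and data collection do not change. The cost is some wording and one table from inclusion dates already held. The two-category share would rest on roughly 450 to 620 subjects instead of 680 under assumed shares of 55% to 75%, with a half-width of about 4 points before any allowance for site clustering.

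Repeating the by-line primary proportion in the common recruitment window is optional only. The slower line would have about 113 to 278 subjects before the 15% loss, fewer than the 289 needed, so it would miss the planned 5-point precision.

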9.2.4 Study Duration

In the METEOR study, the median duration of exposure in subjects receiving cabozantinib was 8.3 months (Inter-Quartile Range 4.2 to 14.6).

PAGE 25 OF 58

Subjects will be followed up to 30 days after discontinuation of cabozantinib with a maximum follow-up per subject of 12 months from treatment initiation, even if the subject continues to receive cabozantinib.

The end of the study will be the date of the last study visit for the last subject in the study.

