9.2.8 Study Discontinuation/Withdrawal

If the subject permanently discontinues cabozantinib before Month 12, he/she will be withdrawn from the study.

The investigator may withdraw the subject from the study at any time for safety reasons or at his/her discretion. A subject may withdraw consent to participate in the study at any time.

In case of permanent treatment discontinuation between Visit 2 and Visit 8, the next visit should be completed along with the Study discontinuation form, approximately 30 days after the last dose of cabozantinib (see Table 1 and Section 9.2.7).

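### Kaplan-Meier medians for AE-driven dose modification and its components would censor stops and deaths that rule out the event; cumulative incidence fits better

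*Protocol*

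**What the plan says.** Section 9.7.2.5.2 names the estimator and the summary: "the Kaplan-Meier method will be used to obtain the estimates of median PFS time, OS rate, median time to end of treatment", and then the median times to first dose modification, each with a 95% CI. There are two families, joined in one sentence: "temporary interruption, reduction or discontinuation) together and for each component separately and median time to any first dose modification". One covers modifications due to AEs (interruption, reduction, discontinuation). The other covers modifications for any reason and adds increases: "median time to any first dose modification (temporary interruption, reduction, increase or discontinuation) together and for each component separately". The endpoint list in the same section repeats the second family. No section mentions competing events, a cumulative incidence function or a censoring rule.

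Section 9.2.8 sets what happens at a permanent stop: "If the subject permanently discontinues cabozantinib before Month 12, he/she will be withdrawn from the study". Section 9.2.4 adds: "Subjects will be followed up to 30 days after discontinuation of cabozantinib with a maximum follow-up per subject of 12 months from treatment initiation". The same section gives the METEOR exposure, where "the median duration of exposure in subjects receiving cabozantinib was 8.3 months (Inter-Quartile Range 4.2 to 14.6" months). Section 9.5 gives 59.8% for dose reduction due to an AE and 70% for interruption, and states: "The rate of treatment discontinuation due to an AE was 9.7% for subjects treated with cabozantinib". Section 7.1 gives median times of 38.0 days to interruption and 55.0 days to first reduction.

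The primary endpoint (section 9.7.2.5.1) is a crude proportion with a Clopper-Pearson interval and does not use Kaplan-Meier.

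**The concern.** A subject who stops for progression, or dies, can never afterwards have an AE-driven interruption, reduction or discontinuation. A subject who stops for any reason can never afterwards have an interruption, reduction or increase. These are competing events. Because such subjects are withdrawn, the natural Kaplan-Meier handling is to censor them, which treats the event as still possible and as likely as in those who remain on treatment. The curve then describes a hypothetical setting in which nobody stops for another reason. The study's aim is to describe actual use.

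The outputs at stake are secondary but close to the research question: how soon, and how often, each type of modification happens in practice. Medians would be too short, and any plotted curve would sit above the crude proportion reported beside it.

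Separately, a median says little about a component that most subjects never experience.

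**Working it through.** **The plan's own figure.** z² × 0.75 × 0.25 / 0.05² = 288.1, so 289 per line; 289/0.85 = 340. The sample size reproduces and is unaffected. The protocol gives no planning figure for the Kaplan-Meier endpoints.

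**Which endpoints have competing events.**

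| Endpoint | Competing events |
|---|---|
| First AE modification, composite | Stop for a non-AE reason; death |
| AE interruption; AE reduction | Any permanent stop; death |
| AE discontinuation | Stop for a non-AE reason; death |
| Any-reason interruption, reduction, increase | Any permanent stop; death |
| Any first modification, together | None from stops (a stop is an event); on-treatment death only |
| Any-reason discontinuation | None from stops; on-treatment death only |

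A temporary interruption does not rule out a reduction, nor the reverse, so neither competes with the other.

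**How common stops are.** Assume a constant stop hazard. From the 8.3-month median, λ = ln 2/8.3 = 0.0835 per month. Off treatment by month 12: 1 − exp(−12 × 0.0835) = 63%. This is a rough fit: it implies quartiles of 3.4 and 16.6 months against the stated 4.2 and 14.6.

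**Formulas, constant hazards.** With event hazard h and competing hazard d:
- Cumulative incidence CIF(t) = h/(h+d) × [1 − exp(−(h+d)t)].
- One minus Kaplan-Meier (1−KM) = 1 − exp(−ht), with median ln 2/h.

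The METEOR percentages are treated as 12-month incidences, which the protocol does not state. Solve CIF(12) for h with d = 0.0835:
- First reduction, 59.8%: h = 0.1472. 1−KM = 83%. Median 4.7 against 6.6 months.
- First interruption, 70%: h = 0.2148. 1−KM = 92%. Median 3.2 against 4.0 months.

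**Front-loaded version.** Assume a fraction π of subjects is ever susceptible, with hazard μ, and that the 55- and 38-day medians apply among subjects with the event (30-day months). Then μ + d = ln 2/(days/30), CIF(t) = π × μ/(μ+d) × [1 − exp(−(μ+d)t)] and 1−KM = π × [1 − exp(−μt)]. With d = 0.0835:
- Reduction: μ = 0.295, π = 0.776. 1−KM = 75% against 59.8%. Median 3.5 against 4.6 months.
- Interruption: μ = 0.464, π = 0.827. 1−KM = 82% against 70%. Median 2.0 against 2.3 months.

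Across both versions the medians are 0.3 to 1.9 months too short.

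**AE-only composite.** True 12-month incidence 75% (the planning value); competing stops assumed at 3%, 5% and 7.5% per month.

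| Competing hazard | 1−KM(12), constant | Median KM / CIF, constant (months) | 1−KM(12), front-loaded | Median KM / CIF, front-loaded (months) |
|---|---|---|---|---|
| 0.03 | 84.7% | 4.42 / 4.85 | 79% | 1.92 / 2.00 |
| 0.05 | 90.0% | 3.61 / 4.11 | 82% | 1.87 / 2.00 |
| 0.075 | 94.8% | 2.82 / 3.29 | 87% | 1.81 / 2.00 |

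The median shift is 13 to 15 days with constant hazards. It is about 3 to 6 days when front-loaded with a 38-day median.

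**AE discontinuation.** h = 0.0835 × 0.097/0.633 = 0.0128 per month.
- 1−KM(12) = 14.2% against 9.7%; the Kaplan-Meier median would lie at 54 months.
- If 9.7% were instead the incidence at 24 months, the 12-month figures would be 10.6% against 7.1%.
- A Kaplan-Meier median at month 12 needs h = ln 2/12 = 0.0578, that is a crude rate of 0.0578/0.0835 × 0.633 = 44%.
- In 1000 simulated studies at 289 subjects per line, and 1000 at 340, the median was never reached.

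**Dose increase.** The protocol gives no rate. For assumed 12-month incidences of 2-20%, 1−KM(12) is 3-31% and no median is reached.

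**The case against.** Several counter-arguments have force.

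- **Scope.** For any first modification taken together, and for any-reason discontinuation, a progression stop is itself the event. A reader might infer that every Kaplan-Meier time-to-modification endpoint is affected. That is wrong, and treating those stops as competing there would discard real events. This stands.
- **Outputs.** For these endpoints the plan reports Kaplan-Meier medians, not incidences; incidence comes from the crude proportion. A reader might infer that the primary result is overstated. It is not. The direct error is in the medians, and in any curve drawn from the same analysis.
- **Line comparison.** A reader might infer that the bias distorts second against third-and-later line. The documents do not say which line has more stops for progression. Kaplan-Meier also answers a different question: with equal AE hazards (0.17 per month assumed) and competing hazards of 0.03 and 0.075, it gives 87% and 4.1 months in both lines. Cumulative incidence gives 77% and 66%, medians 4.4 and 5.2 months, solely because of the stops. Section 7.2 names tolerability by line as an unknown, and Kaplan-Meier is arguably closer to that if censoring is independent. This supports keeping Kaplan-Meier alongside if wanted.
- **Unreached medians.** A median that is not reached is a routine result, not an error, and cumulative incidence would not supply one either. What remains is that the chosen summary is uninformative for that component.
- **Left to the SAP.** No censoring rule is stated. If stopped subjects were kept at risk and event-free to month 12, one minus Kaplan-Meier would equal the cumulative incidence. But the estimator itself is fixed in the protocol, and withdrawal at discontinuation makes censoring the natural reading.

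**Conclusion.** The point holds for the AE-only composite, its three components, and the any-reason components interruption, reduction and increase. Under the natural censoring, first-reduction and first-interruption medians would be about 0.3 to 1.9 months too short. Their 12-month curves would stand about 12 to 23 percentage points above the real-world incidence. The composite median may move by only days to about two weeks. For AE discontinuation the curve would read about 14% against 9.7%, with no median within 12 months; dose increase is probably the same, but its rate is an assumption.

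The direction is firm. The size rests on assumed hazard shapes, on a stop hazard taken from METEOR's median exposure, and on reading METEOR percentages as 12-month incidences. The 70% interruption figure is also not stated to be AE-driven.

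These are descriptive secondary endpoints with no formal testing, so this is a worthwhile improvement to the estimator and not a threat to the study's main result.

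**What to change.** In section 9.7.2.5.2 (and the matching abstract text), for the AE-only composite, its components, and any-reason interruption, reduction and increase:

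- Replace or accompany Kaplan-Meier with Aalen-Johansen cumulative incidence, by line and in total, at fixed times such as months 1, 3, 6 and 12, with 95% CIs.
- Treat as competing events death and any permanent discontinuation that is not itself the event.
- Quote a median only where the cumulative incidence reaches 50%.

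Keep Kaplan-Meier for time to end of treatment, for any first dose modification taken together, and for any-reason discontinuation, and state how an on-treatment death is counted in each.

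Cost: a change of method in the protocol text and the SAP, run in standard SAS procedures. The dates and reasons for modification, the last-dose date and the date of death are already collected (sections 9.3.2 and 9.3.4), so no extra data are needed. The downside is slightly more analysis work and a summary less familiar to readers than a median.
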